## **10. STATISTICAL CONSIDERATIONS**

### **10.1 Study Endpoints, Subsets, and Covariates**

For fasting lipid measurements, the values for the Month 3 analysis time point are defined as the average of Week 13 (Day 85) and Week 14 (Day 92) fasting assessments.

**10.1.1 Efficacy Endpoints**

- Percent change and absolute change from baseline in fasting TG
- Percent change and absolute change from baseline in fasting ANGPTL3
- Fasting lipid measurements, including: non-HDL-C, apoB, HDL-C, apoA-1, VLDL-C, and LDL-C
- Percent change and change from baseline in other fasting lipid measurements including total cholesterol, non-HDL-C, apoB, HDL-C, apolipoprotein A-1 (apoA-1), VLDL-C, and LDL-C
- Postprandial TG change from baseline
- Frequency and severity of patient reported abdominal pain during the treatment period

**10.1.2 Safety Endpoints**

- Adverse events
- Vital signs and weight
- Physical examinations
- Clinical laboratory tests (serum chemistry, hematology, coagulation, urinalysis)
- Electrocardiograms (ECGs)
- Use of concomitant medications

**10.2 Sample Size Considerations**

There is no formal statistical justification for the selected sample size. The sample size is selected based upon prior experience with AKCEA-ANGPTL3-LRX to ensure that the safety, tolerability and efficacy of AKCEA-ANGPTL3-LRX can be explored while minimizing unnecessary subject exposure. In 6 healthy volunteers, AKCEA-ANGPTL3-LRX reported a 63% TG reduction after 6 weeks of administration.

**10.3 Populations**

Safety Set: All subjects who are enrolled and receive at least 1 dose of Study Drug.

PK Set: All subjects who receive at least 1 dose of Study Drug and have at least 1 evaluable PK sample.

**10.4 Definition of Baseline**

Definitions of baseline are given below for the purposes of the final analysis.

For fasting lipid measurements, the baseline is defined as the average of Day 1 pre-dose assessment and the last measurement prior to Day 1.

For other measurements, baseline will be the last non-missing assessment prior to the first dose of Study Drug.

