#### ***6.1.1 Screening***

Written informed consent for the study will be obtained prior to the performance of any study-related procedures including screening procedures. An up to 8-week period is provided for completing screening assessments and determining subject eligibility for the study. Subjects on stable diet known to the investigator and followed at the site may skip the 6-week diet run-in. Safety labs may be re-tested for determination of subject eligibility after consultation with the Sponsor Medical Monitor.

During the screening period, subjects will undergo a medical history and physical examination including vital signs, 12-lead ECG, and have blood and urine samples taken for clinical laboratory testing. Subjects will be screened for HIV, hepatitis B, and hepatitis C.

Eligible subjects will be on a stable low-fat diet (according to local clinical guidelines) beginning at least 6 weeks prior to the first dose of Study Drug. The diet stabilization period may be reduced if the patient is following a stable low fat diet for optimal disease control and disease management prior to screening.

Subjects meeting eligibility criteria at Screening will receive standardized meals in preparation for the pre-dose postprandial analysis to be performed on Day -1.

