### **6.1.2 Treatment Period**

Subjects will be managed on an outpatient basis. Safety and clinical laboratory evaluations as well as blood sampling for PK analysis will be performed periodically throughout the treatment period. Any AEs and concomitant medications will be recorded.

*Postprandial Assessment (Appendix E):* Postprandial assessments will be performed at Day -1 and at Week 14. Subjects will consume standardized pre-cooked meals (lunches and dinners (provided) and instructions for breakfasts and snacks) for the 2 days prior to the post-prandial evaluations. Patients will remain fasted after consuming the standardized pre-cooked meal for the dinner on the evening prior to their visit. Alcohol consumption is not allowed for the 2 days prior to the post-prandial evaluations. On each of the post-prandial evaluation days, following the first blood draw, patients will consume a standardized liquid meal (which represents about a third of the daily caloric requirements) containing a radioisotope tracer, followed by an 9 hour infusion of two stable isotope tracers and serial blood sampling. Patients will receive a standardized pre-cooked meal 9 hrs after consuming the liquid meal, after which they will fast until the 24 hour blood draw the following day.

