## **10.6 Planned Methods of Analysis**

Summary tabulations will be provided for disposition, demographic, baseline, efficacy, and safety data as noted in the following sections.

All eCRF data, lab data, and any outcomes derived from the data will be provided in the patient data listings. Patient data listings will be presented for all patients enrolled into the study. Descriptive summary statistics including n, mean, median, standard deviation, standard error, interquartile range (25th percentile, 75th percentile), and range (minimum, maximum) for continuous variables, and counts and percentages for categorical variables will be used to summarize most data.

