## **14. APPENDICES**

## **Appendix A      Schedule of Procedures**

## Appendix A Schedule of Procedures

Study Period	Screen/ Run-in a	Treatment Period										Post-treatment Follow-up		
		-8 to -1	1	3	5	7	9	11	13	14/ET			18	22
Study Week	-56 To -1	1 b	15	29	43	57	71	85	92	94	95	120	148	176
Visit and Testing Window +/- Days	0	0	2	2	2	2	2	2	2	0	0	3	3	3
Informed Consent	X													
Inclusion/Exclusion Criteria	X	X												
Medical History	X													
Height & Weight c	X	X		X		X			X					X
Vital Signs	X	X		X		X			X			X	X	X
Physical Examination d	X	X		X		X			X					X
12- lead ECG (triplicate)	X	X		X		X			X					X
24-hour urine creatinine clearance and protein	X													
Abdominal Pain Assessment	X	X		X		X			X					X
Urinalysis	X	X		X		X			X			X	X	X
Blood Draw e	Chemistry Panel (+ CPK) f,g	X	X	X	X	X	X	X	X			X		X
	CBC with Differential f,g	X	X	X	X	X	X	X	X			X h	X	X
	Serum Lipid Panel	X	X		X		X		X	X		X	X	X
	PD Panel		X		X		X		X	X		X	X	X
	Coagulation (aPTT, PT, INR)	X	X		X		X			X		X	X	X
	Complement Markers C5A, Bb	X	X							X				
	hsCRP	X	X		X		X			X				X
	Hepatitis B, C, HIV, TSH, Free T 4	X												
	Plasma PK i		X 		X 	X 	X 	X 		X		X	X	X
	Genetic Testing j	X												
	Anti-ANGPTL3-L RX Antibodies		X 		X 		X 			X		X		X
	FSH (women only, if applicable) k	X												
	Serum Pregnancy Test k	X	X		X		X		X	X		X	X	X

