Appendix A Schedule of Procedures *Continued*

Study Period	Screen/ Run-in a	Treatment Period										Post-treatment Follow-up												
		1	3	5	7	9	11	13	14/ET			18	22	26										
Study Week	-8 to -1	1 b	15	29	43	57	71	85	92	94	95	120	148	176										
Study Day	-56 To -1	1 b	15	29	43	57	71	85	92	94	95	120	148	176										
Visit and Testing Window +/- Days	0	0	2	2	2	2	2	2	2	0	0	3	3	3										
HbA1C and delipidated free glycerol	X																							
Archived Serum & Plasma m		X								X				X										
Post-Prandial Assessment	X i									X i	X i	X i												
Platelet aggregation		X		X		X				X				X										
Study Drug Administration		WEEKLY SUBCUTANEOUS ADMINISTRATION OF STUDY DRUG (Week 1 through Week 13)																						
Adverse Events	TO BE COLLECTED FROM TIME OF INFORMED CONSENT TO END OF FOLLOW-UP PERIOD																							
Concomitant Medication	TO BE COLLECTED FROM TIME OF INFORMED CONSENT TO END OF FOLLOW-UP PERIOD																							

All procedures and study samples are to be performed pre-dose at respective visits, unless specified

- a Subject starts the tightly controlled diet, if needed.
- b After 6 weeks on the controlled diet, patients will have baseline measurements and be assessed for qualification of enrollment.
- c Height is only required on Day 1.
- d Full physical exam to be given at Screening and abbreviated physical exam to be given during treatment and follow-up period as indicated to assess changes from screening.
- e Blood samples to be collected after an overnight fast of at least 10 hours and preferably not more than 12 hours, unless tests are repeated for safety reasons.
- f If the platelet value, serum creatinine or liver enzyme tests are uninterpretable (e.g., due to clumping, hemolysis or quantity not sufficient) a repeat blood specimen should be re-drawn as soon as possible (ideally within 7 days). All platelet count results will be reviewed promptly (within 48 hours of receipt) by the Investigator. Any case of a platelet count  $\leq 50,000/\text{mm}^3$  should be reported in an expedited fashion to the Sponsor.
- g If not done as part of a Study Center visit, assessments and procedures to be conducted by either a home healthcare service or the Study Center. Subject Study Center visits must be no more than 4 weeks apart during the treatment period.

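### The fasting lipid baseline in Section 10.4 carries no diet condition, so for a patient who starts the controlled diet at Screening a pre-diet triglyceride value can supply half of it

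*Combined protocol and SAP*

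**What the plan says.** All references are to the current protocol text (Amendment 1).

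- **Baseline.** Section 10.4: "For fasting lipid measurements, the baseline is defined as the average of Day 1 pre-dose assessment and the last measurement prior to Day 1". It names no visit or sample type for the second value and does not mention diet.
- **Lipid sampling before dosing.** In Appendix A the row "Serum Lipid Panel" is marked once in the Screen/Run-in column, which spans Days -56 to -1 with no fixed draw day, and once on Day 1. Inclusion criterion 4 allows repeat TG tests only when the first is below 750 mg/dL.
- **Diet.** Footnote a, on the Screen/Run-in column: "Subject starts the tightly controlled diet, if needed". Footnote b, on the Day 1 column: "After 6 weeks on the controlled diet, patients will have baseline measurements and be assessed for qualification of enrollment". Section 6.1.1 adds an exception: "Subjects on stable diet known to the investigator and followed at the site may skip the 6-week diet run-in".
- **Endpoint.** Section 10.1 defines Month 3 as the "average of Week 13 (Day 85) and Week 14 (Day 92) fasting assessments". Section 10.6.3 summarizes change and percent change in fasting TG to Month 3. It also gives a response rate: serum TG below 750 mg/dL, or a fall of at least 40% from baseline.
- **Day -1.** Appendix E schedules a draw one hour before the test meal on Day -1, collected into EDTA/Orlistat tubes. Patients are fasted at that point (Section 6.1.2).

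**The concern.** The run-in exists so that change is measured from an on-diet level. Both Month 3 samples are taken on diet. If one of the two baseline samples is not, the two ends of the comparison differ in diet as well as in drug.

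If the diet lowers TG, the error always favours the drug, and there is no control arm in which it would show. It reaches percent change in fasting TG, which serves the primary objective, and the 40% limb of the response rate. The limb based on TG below 750 mg/dL does not use baseline and is unaffected. With about three patients, one who crosses the 40% line moves the response rate by 33 points (1/3), unless that patient already responds on the other limb.

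**Working it through.** The plan gives no figure to reproduce: Section 10.2 states that the sample size has no formal justification, and no SD or diet effect appears.

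**Step 1. Which value does the rule select?** Take a patient who starts the diet at Screening and whose first fasting TG is at least 750 mg/dL. No repeat test is called for, and no other serum lipid panel is scheduled until Day 1. The last scheduled serum value before Day 1 is therefore the Screening one. If it was drawn as the diet began, it is a pre-diet value with weight 1/2. Footnote b sits on the Day 1 column and does not change which earlier value Section 10.4 picks up.

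**Step 2. Effect on one patient.** Let d be the fractional TG fall from the Screening draw to Day 1 due to diet, assumed to persist to Month 3. Let e be the true drug reduction. Neither is given for these patients. With Screening TG set to 1:

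- Baseline = (1 + (1 - d))/2 = 1 - d/2
- Month 3 = (1 - d)(1 - e)
- Apparent reduction = 1 - (1 - d)(1 - e)/(1 - d/2)

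At d = 20% and e = 30%: 1 - 0.8 × 0.7/0.9 = 37.8%.

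| Assumed d | e = 0 reads as | e = 30% reads as | e = 60% reads as | Lowest e that reads as 40% |
|---|---|---|---|---|
| 10% | 5.3% | 33.7% | 62.1% | 36.7% |
| 20% | 11.1% | 37.8% | 64.4% | 32.5% |
| 30% | 17.6% | 42.4% | 67.1% | 27.1% |

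The 60% column is the effect cited in Section 2.4 for dose choice. The last column is 1 - 0.6(1 - d/2)/(1 - d).

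**Step 3. Effect on the mean of three.** The excess is (k/3) × (apparent - e), with k patients affected. For k = 1 and d = 20%:

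- e = 0: 11.1/3 = 3.7 points
- e = 30%: 7.8/3 = 2.6 points
- e = 60%: 4.4/3 = 1.5 points

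Over d = 10% to 30% and k = 0 to 3, the excess runs from 0 to 17.6 points at e = 0, 0 to 12.4 at e = 30%, and 0 to 7.1 at e = 60%. Each upper end needs all three patients affected and d = 30%.

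**Step 4. Noise.** Assume a within-patient CV of 20%, 30% or 40%, independent lognormal values, a true 30% fall and a two-value Month 3. By simulation, the SD of one patient's percent change is 14.3, 22.1 or 30.8 points with a two-value baseline, and 17.9, 28.5 or 40.9 with Day 1 alone. For one affected patient at d = 20% and e = 30%, switching that patient to Day 1 alone raises the root mean square error of the three-patient mean. It goes from about 8.1 to 9.2 points at CV 20%, and from about 17.3 to 21.2 at CV 40%.

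**The case against.** **The intent is already on paper.** Footnote b places baseline measurements after six weeks of diet, footnote a does not tie the panel to the day the diet starts, and a panel drawn late in the run-in complies with the schedule. This stands as evidence of intent. It does not bind Section 10.4, because nothing requires the late draw.

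**The Day -1 draw may be the last measurement.** Taken literally, Section 10.4 could mean the fasted pre-meal sample, which is on diet. In Section 10.6.3 the word serum appears only in the responder sentences, not in the percent-change sentence. Against this, Section 10.4 does not name that sample, it goes into EDTA/Orlistat tubes, and the scheduled lipid panel is serum. Both readings remain open. A reader might infer that the plan commits to a pre-diet baseline; the documents do not support that.

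**Perhaps nobody is affected.** Patients on a known stable diet may skip the run-in, and Section 2.1 describes very high TG in this disease despite extreme fat restriction. This stands: k may be zero. A claim that the trial's TG result will be inflated would go beyond the documents.

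**The bias is small beside the noise.** At d = 20% and e = 30%, one affected patient adds 2.6 points. The standard error of the mean of three is about 14.3/√3 = 8.3 to 30.8/√3 = 17.8 points. This also stands, and the analysis is descriptive. The case for change is removal of a one-directional error, not a gain in precision.

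**A reader can look.** Section 10.6 promises that "All eCRF data, lab data, and any outcomes derived from the data will be provided in the patient data listings". That exposes the Screening and Day 1 values, but the summaries would not show the problem.

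**Off-drug lipids at Days 120, 148 and 176 could help.** In part they can. A reader might use the 3 to 5 week terminal half-life to calculate how much drug remains at Day 176. Section 2.3.4 describes a multi-phasic decline, so that sum would give a fraction of a terminal-phase level only. No such figure is relied on here.

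**Conclusion.** The gap in the rule is clear; the size of its effect is not. The bias arises only in run-in patients whose Screening panel is drawn before or early in the diet, and only if that panel, rather than the Day -1 draw, supplies the second value. It is zero for patients already on a stable diet and for panels drawn late in the run-in.

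The figures rest on assumed values of d, persistence of the diet effect to Month 3, and an assumed number of affected patients. Importance is minor to moderate: this is a descriptive study of about three patients, but the baseline feeds its main efficacy summary and no control arm would reveal the error. It should be corrected because the correction is cheap.

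**What to change.** In Section 10.4, require both fasting lipid baseline values to be fasting serum values taken on the stable diet, in line with footnote b, and name the sample that supplies the second one. That also settles the status of the Day -1 draw.

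For run-in patients, add one serum lipid panel to Appendix A after diet stabilization and before dosing. State how it relates to the standardized meals eaten "for the 2 days prior to the post-prandial evaluations". Patients already on a stable diet keep the Screening panel.

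If no on-diet second value exists, show the result with Day 1 alone and with the current definition side by side. Day 1 alone should not simply replace the current definition. It removes the diet bias but is noisier (Step 4), and under Appendix E the Day 1 sample follows a test meal by 24 hours.

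In the listings, show run-in status (done, shortened or skipped) and the Screening draw date beside the TG values.

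The cost is one or two sentences, one extra serum sample per run-in patient, and a possibly smaller reported TG reduction. One asymmetry remains: Day 1 follows standardized meals, whereas Days 85 and 92 come before the Week 14 ones.

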Section 6.2	
WAS:  Blood chemistry and urine samples (excluding 24-hour urine collection) should be taken <del>be taken</del> after fasting...
 
IS:  Blood chemistry and urine samples (excluding 24-hour urine collection) should be taken after fasting...
	Error corrected
Section 8.5.1	
WAS:  All patients will have liver chemistry tests monitored every 2 weeks during and treatment and follow-up Period.
 
IS:  All patients will have liver chemistry tests monitored every 2 weeks during the treatment and follow-up Period.
	Error corrected.
Section 8.10.1	
WAS:  Fibrates within 8 weeks of screening
 
IS:  Not applicable
	The inconsistency of this section was corrected to align with all other sections.
Section 9.4.1	
WAS:  Attention: [REDACTED]  Email: [REDACTED]  Fax: [REDACTED]
	The safety reporting vendor was changed.

	IS: [REDACTED] [REDACTED] – USA: Telephone: [REDACTED] or [REDACTED] Facsimile: [REDACTED] or [REDACTED] e-mail: [REDACTED]	
Section 10.6.3	
WAS:
 
Response rate of patients with fasting plasma TG < 750 mg/dL or achieving fasting TG <math>\geq</math> 40% reduction from baseline at Month 3 will be summarized. Response analysis will also be conducted using a range of fasting plasma TG thresholds for determination of responder status.
 
IS:
 
Response rate of patients with fasting serum TG < 750 mg/dL or achieving fasting TG <math>\geq</math> 40% reduction from baseline at Month 3 will be summarized. Response analysis will also be conducted using a range of fasting serum TG thresholds for determination of responder status.
	The matrix in which TG are measured in serum.
Section 11.1	
WAS:
 
Not applicable
 
IS:
 
The sponsor shall maintain all records referred to in the applicable Regulations for a period of 25 years.
	Requested by Health Authority

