**5.1 Inclusion Criteria**

1. Must have given written informed consent (signed and dated) and any authorizations required by local law and be able to comply with all study requirements.
2. Males or females aged  $\geq 18$  years old at the time of informed consent.
3. Genetically confirmed homozygote or compound heterozygote for known null loss-of-function mutations in the LPL gene.
4. Fasting TG  $\geq 750$  mg/dL (8.4 mmol/L) at Screening. If the fasting TG  $< 750$  mg/dL up to 2 additional tests may be performed in order to qualify.

5. Willing to follow a diet comprising  $\leq 20\text{g}$  fat per day during the study.
6. Females: must be non-pregnant and non-lactating and either:
  - i. Surgically sterile (e.g., tubal occlusion, hysterectomy, bilateral salpingectomy, bilateral oophorectomy);
  - ii. Post-menopausal (defined as 12 months of spontaneous amenorrhea in females  $> 55$  years of age or, in females  $\leq 55$  years, 12 months of spontaneous amenorrhea without an alternative medical cause and FSH levels in the postmenopausal range for the laboratory involved);
  - iii. Abstinent\* or,
  - iv. If engaged in sexual relations of child-bearing potential, agree to use 2 highly effective contraceptive methods (refer to [Section 6.3.1](#)) from the time of signing the informed consent form until at least 13 weeks after the last dose of Study Drug (AKCEA-ANGPTL3-LRX).
7. Males: Surgically sterile or if engaged in sexual relations with a female of child-bearing potential, subject is utilizing an acceptable contraceptive method (refer to [Section 6.3.1](#)) from the time of signing the informed consent form until at least 13 weeks after the last dose of Study Drug (AKCEA-ANGPTL3-LRX).

\* Abstinence is only acceptable as true abstinence, i.e., when this is in line with the preferred and usual lifestyle of the patient. Periodic abstinence (e.g., calendar, ovulation, symptothermal, post-ovulation methods), declaration of abstinence for the duration of a trial and withdrawal are not acceptable methods of contraception.

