### ***10.6.3 Efficacy Analysis***

Percent change and change from baseline to Month 3 in fasting TG will be summarized. Response rate of patients with fasting serum TG < 750 mg/dL or achieving fasting TG  $\geq$  40% reduction from baseline at Month 3 will be summarized. Response analysis will also be conducted using a range of fasting serum TG thresholds for determination of responder status.

Percent change and change from baseline to Month 3 will also be summarized by treatment group for other fasting lipid measures including ANGPTL3, non-HDL-C, apoB, HDL-C, apoA-1, VLDL-C, and LDL-C, total cholesterol, and fasting total apoC-III.

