### Post-prandial Sampling (Blood) Schedule

Study Day	D -1 a	D1	D94	D95
Visit Window +/- Days	0	0	0	0
	-1 hr pre-prandial, and 0, 1, 2, 3, 4, 5, 6, 7, 8, and 9 hrs post prandial	24 hrs post-prandial /pre SC injection	-1 hr pre-prandial, and 0, 1, 2, 3, 4, 5, 6, 7, 8, and 9 hrs post-prandial	24 hrs post-prandial

a There is a range for this visit, it should happen prior to and as close as possible to Day 1.

Plasma samples may also be used for profiling of drug binding proteins, bioanalytical method validation purposes, stability and metabolite assessments, or to assess other actions of AKCEA-ANGPTL3-LRX with plasma constituents.

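### For a patient whose usual TG is near 750 mg/dL, half of the TG baseline is a Screening value selected for being high, so the change from baseline shows on average a fall that is not drug effect

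*Combined protocol and SAP*

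**What the plan says.** All references are to the protocol as changed by Amendment 1.

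- **Entry.** Inclusion criterion 4 (Section 5.1) requires a fasting TG of at least 750 "mg/dL (8.4 mmol/L) at Screening". If the value is lower, "up to 2 additional tests may be performed in order to qualify".
- **Baseline.** For fasting lipids, Section 10.4 says "the baseline is defined as the average of Day 1 pre-dose assessment and the last measurement prior to Day 1". It does not name the visit or the sample type of the earlier measurement, and it does not exclude a value used for entry.
- **Schedule.** In Appendix A the row "Serum Lipid Panel" is marked at Screening and Day 1, with nothing between; the next panel is Day 29.
- **Endpoint.** Section 10.1 has Month 3 "defined as the average of Week 13 (Day 85) and Week 14 (Day 92) fasting assessments". Section 10.6.3 says "Percent change and change from baseline to Month 3 in fasting TG will be summarized", and adds a responder summary that includes a reduction of at least 40%.
- **Sample type.** Section 10.6.3 refers to serum TG. The amendment's reason for that change reads "The matrix in which TG are measured in serum".
- **Another pre-dose fasting draw.** Appendix E has a sample one hour before the meal at the pre-dose postprandial visit, nominally Day -1. Its footnote says "There is a range for this visit, it should happen prior to and as close as possible to Day 1". Blood for that series goes into EDTA/Orlistat tubes.

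Section 3.3 plans about 3 patients, all on active drug.

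**The concern.** Retesting happens only after a value below 750 and has no purpose once a value passes. The last Screening TG of an enrolled patient is therefore the one that passed, and it cannot be below 750. If it is the last measurement before Day 1, half of the baseline is truncated from below, any failed lower values drop out, and the Month 3 values carry no such selection. A patient whose TG varies around a level near 750 will then tend to show a fall even if nothing has changed.

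A control arm would show the same fall and cancel it. This study has none, so regression to the mean is counted as drug effect. It enters the percent change, the absolute change and the 40% responder limb, all of which serve the primary objective of TG reduction.

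**Working it through.** The plan gives no alpha, power or standard deviation (Section 10.2 says there is no formal justification), so there is no stated figure to reproduce. The check asks how large a fall appears with no drug effect.

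**Inputs from the documents:** threshold 750 mg/dL and up to three tests (Section 5.1); baseline is the mean of the qualifying value and Day 1 (Section 10.4, read with Appendix A); Month 3 is the mean of Days 85 and 92 (Section 10.1).

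**Assumptions:** TG is lognormal around a patient's usual (median) level L, independent between visits, with a within-patient CV of 20, 30 or 40%.

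**Formulas.** Let s = sqrt(ln(1 + CV²)) and z = ln(750/L)/s.

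- Chance of passing one test: P1 = Φ(-z). Chance within three tests: 1 - (1 - P1)³.
- Mean of an unselected value: L × sqrt(1 + CV²).
- Mean of the qualifying value: L × sqrt(1 + CV²) × Φ(s - z)/Φ(-z).

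**Worked case, L = 700, CV 30%.** s = sqrt(ln 1.09) = 0.294 and z = ln(750/700)/0.294 = 0.235.

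- P1 = Φ(-0.235) = 0.407; within three tests, 1 - 0.593³ = 0.79.
- Mean unselected value: 700 × 1.044 = 731 mg/dL.
- Mean qualifying value: 731 × Φ(0.059)/0.407 = 731 × 0.523/0.407, about 940 mg/dL.
- Mean baseline: (940 + 731)/2, about 835. Mean Month 3: 731. The spurious difference is about -104 mg/dL, and -104/835 is about -12%.

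**Simulation** (400,000 patients per cell, no drug effect), median percent change with the baseline as written:

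| Usual TG (mg/dL) | CV 20% | CV 30% | CV 40% |
|---|---|---|---|
| 700 | -10 | -13 | -16 |
| 800 | -6 | -9 | -12 |
| 1,000 | -1.3 | -3.7 | -6.4 |
| 1,500 | -0.1 | -0.4 | -1.2 |

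At 3,000 mg/dL the median is about 0. With a baseline of Day 1 plus a value not used for entry, the median is 0 throughout. Medians are shown because the mean of a ratio is pulled slightly upward by noise even when the baseline is unselected.

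**Responders.** At L = 700 and CV 30%, about 8% of enrolled patients reach a 40% reduction with no drug effect, against 4.2% with an unselected baseline.

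**Effect on three patients.** One patient at L = 700 moves the group average by roughly 10/3 to 16/3, or about 3 to 5 percentage points. This is only a guide, since it divides medians.

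**Role of retests.** Given that a value passed, its distribution is the same whether it was the first test or the third. At L = 600 and a log-scale SD of 0.25, the mean change is -15.4% with one test allowed and -15.3% with up to three. What changes is the share who qualify: 18.6% against about 46%.

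**The case against.** **The Day -1 draw could be the last measurement.** Section 10.4 names neither visit nor sample type. The postprandial series includes a fasting draw just before Day 1, and that value is not selected on 750. If it is the one meant, the bias disappears. The wording permits this reading, so a reader should not infer that a biased baseline is beyond dispute. The other evidence favours the Screening panel: efficacy TG is serum, the postprandial samples are EDTA/Orlistat plasma, and the lipid-panel row has no mark between Screening and Day 1. On either reading Section 10.4 needs to name the visit.

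**Few patients will be affected.** Criterion 3 requires null LPL mutations on both alleles, and Section 2.1 gives typical FCS values of 1,500 to 15,000 mg/dL despite dietary fat restriction. This stands, and it limits the point to patients near the cut-off. The plan does admit them, and the retest rule operates only for patients with a value below 750.

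**The bias is small beside the noise and the expected effect.** This also stands. With three patients and a log-scale SD of 0.25 to 0.35, the standard error of the mean change is roughly 14 to 20 points, and the reference effect in Section 10.2 is 63%. But noise averages to zero and this bias does not. The listings promised in Section 10.6 should show failed Screening values, but they do not correct the summary.

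**Conclusion.** The point holds for patients whose usual TG is near 750 mg/dL, on the natural reading of Section 10.4 with Appendix A. The median spurious fall is about 10 to 16% at 700 mg/dL, 6 to 12% at 800, 1 to 6% at 1,000, and 0 to 1% from 1,500 upward. These sizes rest on an assumed CV and on independence between visits.

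Four stronger inferences are not supported:

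- That the bias explains a large effect. It cannot produce a fall of about 60%, and it is close to zero in the documents' typical FCS range.
- That it always favours the drug. It does so on average: with no drug effect, 28 to 31% of qualifiers at 700 and 36 to 38% at 800 still show a rise.
- That retests enlarge the fall. They admit more near-threshold patients and leave the fall in a given patient unchanged.
- That a designated primary endpoint is biased. Section 10.1.1 labels none as primary; fasting TG change is listed first and serves the primary objective.

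The change is worth making because it is cheap and the study has no control arm to absorb the bias.

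**What to change.** In Section 10.4, state that a Screening TG used to meet criterion 4 is not part of the analysis baseline. Define the fasting TG baseline as the average of the Day 1 pre-dose value and the fasting value drawn one hour before the meal at the pre-dose postprandial visit, measured in serum. Appendix E starts the tracer infusion at the same hour, so the text should say that the serum tube is drawn before it begins.

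**Cost:** one sentence and one serum tube at an existing draw. There is no added visit and no change to eligibility or treatment.

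**Downside:** the two baseline values may fall on consecutive days after standardized meals, whereas Month 3 uses Days 85 and 92, a week apart and before the second set of meals is supplied. The mismatch is limited, because the Day 1 value already follows those meals under the current plan. A sensitivity summary using the baseline as now defined would show whether the choice matters.

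**Partial fallback:** averaging all Screening values, including those below 750, is weaker. At 700 mg/dL and CV 30% it reduces the median fall from about 13% to about 7.5%, and it does nothing for a patient who passes on the first test.
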